Patient aged 18 years or above will be included if they undergo abdominal colorectal operation including colorectal cancer case and non-colorectal cancer case such as perforated diverticulitis, trauma, and so on. Patients with cognitive impairment and/or with known allergic reactions to silver, hydrofibre or hydrocolloid and/or with non-closed wound immediate after operation will be excluded.

Subjects will be randomly assigned to use occlusive ionic silver-containing dressing (experimental group) or conventional gauze dressing (control group) with equal probability. Blocked randomization will be carried out by an independent party using computer-generated random number sequences (www.randomization.com) in random blocks of two, four, six and eight, allocated in sequentially numbered, sealed opaque envelopes. Those envelopes would be prepared and placed in each surgical ward.

Data collection procedure

On the day of admission, or an emergency operation is offered, written informed consent will be obtained from all eligible patients. Patients will be arranged by an independent primary nurse in two groups, the experimental and control group, according to the designed block randomized sequence. Relevant dressing materials will be prepared by the primary nurse and bring to the operation theatre. In order to blind the subject, the incisional wound will be covered by ionic silver containing and hydrocolloid dressing with gauze covered on the top for the experimental group, whereas only gauze dressing will be applied for the control group.

Patient's case doctor will be responsible to document in data collection form, if there are surgical site infection occur. A research team is responsible for the data collection. Data obtained includes age, gender, pre-operative albumin level, pre- and post-operative sepsis status, operation class (elective or emergency), operation duration, number of operation, wound classification (clean, clean-contaminated, contaminated, and dirty), types of stoma raised (colostomy or ileostomy), the use and length of duration of antibiotics (pre op and post op). Subjects will be assessed for SSI on Day 3, 15 and 30 after operation in clinical area and followed by phone interviews. During hospitalization, patient's case doctor, who are independent to the study, will be responsible for outcome assessment. After patient discharge, patient will be provide the information of SSI status. Data will be collection by

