Silver dressing RCT – protocol (Version 5; 14 September 2017)

research team via phone contact, patient will be blind to the study as well. Carers of the patient, who are blind to the study, will be interviewed if the patient is unable to describe their surgical site condition.

Outcomes

Primary outcome is the SSI on day 30 after operation, whereas secondary outcomes are day 3 and 15 SSI after operation. In view of updating patient's condition after the operation and removal of stitches, the secondary outcomes are decided on day 3 and 15 after operation. Assessment of SSI will adopt the basis of criteria developed by the Centers for Disease Control and Prevention (CDC) [17].

Statistical analysis

SSI incidence and relative risk with 95% confidence interval will be computed for the experimental and control groups. Differences in distribution of the clinical data and the development of an SSI in control and experimental groups were evaluated using Pearson's chi-square test, Fisher's exact test, independent t-test or Mann-Whitney U test, where appropriate. Statistical analyses will be performed using SPSS 22.0 for Windows (IBM Corp., Armonk, New York). A p value <0.05 will be regarded as statistically significant.

Sample size estimation

With reference to our previous internal audit, we might assume the day 30 SSI incidence in the experimental group and control group as 20% and 40%, respectively. Using PASS 13 for sample size calculation, the number of subjects needed in both groups will be 80 with a power of 0.8 and a significance level of 0.05. Assuming the response rate to be 80%, the total sample size required will be 200. It is estimated that the ratio of eligible patients in A4 ward, B4 ward and CD4 ward will be around 1:2:3, therefore the number of subjects needed will be 34, 66 and 100, respectively.

Ethical consideration

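### A 30-day life-table incidence would use the partial follow-up of patients lost before day 30, at little cost; how much it gains depends on when they are lost

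*Protocol*

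**What the plan says.** Outcomes: "Primary outcome is the SSI on day 30 after operation, whereas secondary outcomes are day 3 and 15 SSI after operation". Data collection procedure: "Subjects will be assessed for SSI on Day 3, 15 and 30 after operation in clinical area and followed by phone interviews".

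Statistical analysis: "SSI incidence and relative risk with 95% confidence interval will be computed for the experimental and control groups", with chi-square or Fisher tests for the comparison of SSI. No method for incomplete follow-up is named, and nothing is said about a patient who has no day-30 contact.

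Sample size estimation: the investigators "assume the day 30 SSI incidence in the experimental group and control group as 20% and 40%, respectively"; "the number of subjects needed in both groups will be 80 with a power of 0.8 and a significance level of 0.05"; and "Assuming the response rate to be 80%, the total sample size required will be 200". The Abstract has all 200 patients recruited and randomised.

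Ethical consideration: patients may withdraw at any time, and those who develop an SSI stay in the study and are recorded.

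**The concern.** If 200 are randomised and 160 are counted on for day 30, about 40 patients are allowed to have no day-30 result. Three contacts are planned, so some of the 40 may have been seen, free of infection, on day 3 or day 15. A proportion among day-30 responders cannot use that information, although in the hospital's own audit most SSIs had appeared by day 15.

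The other way to form a crude proportion is worse. An SSI found on day 15 is a known event and, under Ethical consideration, stays in the data. An infection-free patient lost after day 15 has no day-30 value. Keeping the first and dropping the second removes only non-events from the denominator, so both incidences come out too high. At stake are some precision in the primary comparison and the accuracy of the reported incidences.

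**Working it through.** **Inputs from the protocol.** 20% versus 40%, 80 per group, power 0.80, alpha 0.05, 80% response, total 200 (Sample size estimation). Cumulative SSIs at days 3, 15 and 30: gauze 1, 8, 9 of 17; silver 2, 14, 19 of 95 (Table 1).

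**Assumptions.** 100 randomised per arm; 20% lost in each arm, unrelated to SSI; no deaths; audit timing holds in the trial. The timing of loss is not given, so a range is shown.

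**1. The plan's own figure.** Two-sided, unpooled variance: n = (1.960 + 0.842)² × (0.2×0.8 + 0.4×0.6)/0.2² = 7.85 × 0.40/0.04 = 78.5. The arcsine formula gives 80.3 and the pooled formula 82. Pooled power at 80 per group is 0.794. Then 160/0.8 = 200. The stated sample size reproduces.

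**2. Event timing.** By day 3: (1+2)/28 = 10.7%. By day 15: (8+14)/28 = 78.6% (gauze 8/9 = 88.9%, silver 14/19 = 73.7%).

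**3. Keeping known SSIs and dropping infection-free losses, all loss after day 15.**
- Control: events 0.4×0.786 + 0.4×0.214×0.8 = 0.383; infection-free 0.6×0.8 = 0.480; incidence 0.383/0.863 = 44%.
- Silver: events 0.2×0.786 + 0.2×0.214×0.8 = 0.191; infection-free 0.8×0.8 = 0.640; incidence 0.191/0.831 = 23%.
- Relative risk 0.230/0.444 = 0.52 against a true 0.50.

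**4. Precision, all loss after day 15.** The Greenwood variance of the 30-day incidence is S² × Σ d/[r(r−d)], with S the infection-free proportion at day 30, r the number at risk and d the events in each interval.
- Control: to day 15, with no loss yet, 0.3143/(100×0.6857) = 0.00458. From day 15 to 30, r = 68.57×0.8 = 54.9 and risk 0.125, so 0.125/(54.9×0.875) = 0.00260. Variance 0.36 × 0.00719 = 0.00259.
- Silver: 0.1571/(100×0.8429) = 0.00186. Then r = 67.4 and risk 0.0508, giving 0.00079. Variance 0.64 × 0.00266 = 0.00170.
- Sum 0.00429, against 0.16/80 + 0.24/80 = 0.00500 for responders only. Equivalent complete patients per arm: 80 × 0.00500/0.00429 = 93.
- Power Φ(0.2/√0.00429 − 1.96) = Φ(1.09) = 0.86, against Φ(0.2/√0.00500 − 1.96) = Φ(0.87) = 0.81.
- Log relative risk: SE = √(0.00170/0.04 + 0.00259/0.16) = 0.242, against √(0.00200/0.04 + 0.00300/0.16) = 0.262. Around a relative risk of 0.50 the 95% interval is about 0.31 to 0.80 instead of 0.30 to 0.84.

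**5. Simulation over the range of loss timing.** 20,000 trials per row, audit timing pooled or by arm, same unpooled test for both estimators.

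| 20% lost | Responders-only power | Life-table power | Equivalent patients per arm (responders-only 80) | Incidences if known SSIs are kept and infection-free losses dropped |
|---|---|---|---|---|
| never contacted | 0.80 | 0.80 | 80 | 20% vs 40% |
| all after day 3 | 0.80–0.81 | 0.81 | 81 | 20.5% vs 41% |
| half after day 3, half after day 15 | 0.80 | 0.84 | 87–88 | 22% vs 43% |
| all after day 15 | 0.81 | 0.86–0.87 | 93–94 | 23% vs 44–45% |

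With the pooled (chi-square) test, responders-only power is 0.79–0.80. The life-table estimates stay at 20% and 40% in every row. The type I error of the life-table test at 30% versus 30% was 0.052–0.053.

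**The case against.** The plan is coherent as it stands: a binary outcome at a fixed day, a relative risk, a standard test, and a sample size inflated so that about 0.80 power survives the allowance. Nothing promised is missed. That stands, and it is why this is an improvement and not a correction.

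A reader might infer more than the protocol supports:
- *That patients lost early contribute nothing.* The protocol does not say they are dropped, and its handling of missing day-30 results may sit in an analysis plan not seen here. Even under a responders-only analysis they count in the day-3 and day-15 outcomes.
- *That the trial expects to lose 20% after randomisation.* The response rate is undefined. Randomising all 200 makes this the natural reading, but when and why patients are lost is not stated. Some may have nothing to recover: dressings are allocated before surgery, and a wound left open after it is an exclusion.
- *That a life table recovers the lost information.* It does so only in part. Someone who cannot be reached by phone may miss both later contacts, and loss after day 3 recovers about one patient per arm.
- *That the comparison is seriously biased.* The upward bias needs a particular way of counting and barely moves the relative risk.

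Plain censoring also has a fault of its own. The population includes emergency surgery and perforated diverticulitis, so some patients may die before day 30. Treating them as still at risk overstates the incidence. The fix has to deal with this.

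**Conclusion.** The point holds as a low-cost improvement; the sample size and the stated analysis contain no error. The benefit ranges from nothing to about 13 or 14 of the 20 lost patients per arm, and the top of that range needs every loss to fall after day 15. The bias in the incidences, at most about 3 to 5 percentage points, arises only if known SSIs are kept while infection-free losses are left out.

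The conclusion rests on reading the response allowance as loss after randomisation, on loss being unrelated to later SSI given status so far, and on event timing from 28 SSIs in a non-randomised audit, only 9 of them under gauze. In the scenarios computed, the life table never had lower power than the responders-only analysis.

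**What to change.** In Statistical analysis, state that:
- the 30-day cumulative SSI incidence in each arm is estimated by a life table over the day 3, 15 and 30 contacts, including all randomised patients with any follow-up;
- patients without SSI are censored at their last contact, and death without SSI is a competing event (cumulative incidence), not censoring;
- the relative risk and its 95% interval come from these estimates, with the variance of the log relative risk taken as V_E/F_E² + V_C/F_C², where F is the 30-day incidence and V its variance in each arm;
- the crude relative risk among day-30 responders is shown as a sensitivity analysis.

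The cost is a few sentences, a date of last contact and of any death for each patient, and slightly more analysis work. No extra visits or patients are needed. The downside is the assumption that loss is unrelated to later SSI given status so far, which is weaker than what a responders-only analysis needs but still cannot be tested from the data.
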